Evaluation of Routine Administration of Glycerin Suppositories to Improve Bowel Function in Patients with Uncomplicated Gastroschisis

NCT03355326

Last date of Revision 5/7/2018

Last date of Approval 4/1/2020

NCT03355326

Introduction/Background:

Gastroschisis is a congenital defect of the abdominal wall that leads to evisceration of various amounts of the abdominal organs. The mainstay of therapy is restoring continuity of the abdominal wall, either through primary closure or with a synthetic graft when primary closure is not feasible. Closure of the abdominal cavity is confounded by prenatal loss of abdominal domain coupled by resultant swelling of the abdominal viscera due to prenatal exposure to amniotic fluid. Additionally, some patients with gastroschisis have other concomitant abnormalities of the bowel (termed complicated gastroschisis) that require additional surgical intervention. It is well established that bowel function after repair of gastroschisis is impaired due to the aforementioned pathologic processes. Previous studies have shown that the time from surgery to attaining full nutrition through enteral means is a predictor for morbidity in this population. Numerous therapeutic interventions have been proposed to help hasten bowel function and decrease the time to tolerance of total enteral nutrition. A common, but unproven, technique is the use of glycerin suppositories to stimulate bowel function.

Study Procedures:

The purpose of this study will be to determine whether routine use of glycerin suppositories improves bowel function as measured by time to full enteral feeds (primary outcome: defined as enteral feed volume ≥120mL/kg/day with appropriate weight gain) in neonates with uncomplicated gastroschisis. Additional secondary outcomes that will be measured include time to first bowel movement, length of hospital stay, infectious complications, days on total parenteral nutrition (TPN), post-operative days on TPN, sequela of long term TPN administration, and post-operative complications.

After obtaining consent, patients will be randomized (utilizing a block technique) into two groups: the treatment group and the control group. Consent and randomization will occur the day of surgery or preceding surgery with the operating surgeon blind to the treatment arm prior to operation. A newly developed study-specific standardized feeding protocol that has been adopted by all pediatric general surgeons at Riley Hospital for Children will be used on all study participants. Signs of feeding intolerance are outlined in the attached feeding protocol. The treatment group will undergo administration of a glycerin suppository beginning the day after abdominal closure and daily until reaching full enteral feeds. Time to first stool (secondary outcome) will also be monitored and recorded. Clinical nursing staff often will report very small bowel movements as "smears". These will be noted in the study database but will not be considered a first bowel movement. If at any point during treatment the patient develops significant rectal bleeding, suppository administration will be discontinued, and the patient will be removed from the study. The control group will not receive routine glycerin suppositories until full enteral feeds are obtained and will be based upon attending preference thereafter. Weaning of TPN during advancement of enteral feeds will be based upon attending preference tholestasis

NCT03355326

(secondary outcome) will also be monitored/recorded, these labs are normally drawn in this patient population and no additional labs/blood draws will be required for this study

Inclusion/Exclusion Criteria:

Inclusion criteria:

-Gestational age >33 weeks at time of delivery

-Weight >1900g at time of delivery

-Transfer of patient to Riley Hospital for Children prior to any abdominal surgery

Exclusion criteria:

-Neurological Congenital malformations or those known to impair intestinal motility

-Identification of a secondary gastrointestinal abnormality requiring surgical intervention

-Cyanotic heart disease

Power Analysis/Recruitment Period

Assuming the average time to full enteral feeds in the control group will be approximately 21 days with a standard deviation of 3 days and a power $(1-\beta)$ of 0.8, the study will need to enroll thirty-seven (37) in each study arm to detect a difference of two days between groups (two sided test with an $\alpha = 0.05$). After reaching this enrollment, that data from each group will be analyzed for normality and if found to be normal, student's t-tests will be performed to determine significance for the primary outcome variables. If the resulting data is not normally distributed, Wilcoxon ranked-sum tests will be performed. Data analysis will be completed by [name]., M.P.H.

The average number of uncomplicated gastroschisis patients admitted to Riley Hospital for Children is approximately 20 per year. Assuming 80% enrollment (i.e. 44 patients enrolled) with an 85% retention rate to completion (i.e. 37 patients completing the study), the study period will be approximately 5.5 years.

Participant Privacy/Data Safety

All data obtained for use in this study will be abstracted from clinical (medical record) and entered on to a RedCap database built explicitly for this research study. Data entry will occur on the private/encrypted pediatric general surgery research computer, which is available only in the Pediatric General Surgery office within the physical/technical infrastructure of Indiana University Health. Additionally these computers are independently password-protected and all access to the office is

NCT03355326

limited to staff only and is continuously supervised. All office doors are locked during non-business hours. Patient names will never be used in the research database in order to help reduce the risk of loss of confidentiality. All physical charts will be reviewed (if needed) in this office and only in this office and delivered immediately back to their respective sites upon completion of review. Paper records will be locked within the pediatric general surgery research office at all times.

NCT03355326

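### The primary endpoint includes a weight-gain condition that the supplied text does not define, and no masking is stated after surgery, so a judgement made with the arm known can move the primary date

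*Combined protocol and SAP*

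**What the plan says.** Study Procedures defines the primary outcome, time to full enteral feeds, as "enteral feed volume ≥120mL/kg/day with appropriate weight gain". Both limbs must be met. The text gives no rate of gain, observation window, reference or assessor for the second limb.

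On masking, the same section says only that consent and randomization take place on or before the day of surgery, "with the operating surgeon blind to the treatment arm prior to operation". The treatment arm then has "administration of a glycerin suppository beginning the day after abdominal closure and daily until reaching full enteral feeds". For controls, "The control group will not receive routine glycerin suppositories until full enteral feeds are obtained". No placebo, sham, masked assessor or adjudication is described.

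Two statements bear on how much discretion there is during feeding. All participants follow a common plan: "A newly developed study-specific standardized feeding protocol that has been adopted by all pediatric general surgeons". Its content is described in one sentence: "Signs of feeding intolerance are outlined in the attached feeding protocol". Against that, "Weaning of TPN during advancement of enteral feeds will be based upon attending preference".

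On data capture, Participant Privacy/Data Safety says: "All data obtained for use in this study will be abstracted from clinical (medical record". It does not say whether the abstractor knows the arm.

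**The concern.** Because the two limbs are joined, an infant who is already at the volume threshold reaches the endpoint only when the weight gain is accepted as adequate. If that call rests on judgement, whoever makes it can know from the bedside or the chart whether the infant is receiving suppositories. The treatment-arm suppositories run until the endpoint is reached, so the last recorded dose could itself be taken to mark the endpoint date.

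The trial is sized for a two-day difference, so a small systematic difference between arms in when weight gain is accepted would be a sizeable part of the target. It could create an apparent effect or hide a real one. Neither the planned t-test nor the Wilcoxon test can tell such a shift from a treatment effect.

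The protocol does supply a counting rule for a secondary outcome: smears do not count as a first bowel movement. The supplied text has no comparable rule for the weight-gain part of the primary outcome.

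**Working it through.** **Inputs from Power Analysis/Recruitment Period:** control mean 21 days, SD 3 days, difference 2 days, two-sided alpha 0.05, power 0.80, 37 per arm, Student's t-test if the data are normal. **Assumed, not in the documents:** a constant shift *b* in one arm's recorded date relative to the other, with the SD unchanged.

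**1. The plan's own figure.** Normal approximation: n = 2 × (1.960 + 0.842)² × 3² / 2² = 35.3, rounded up to 36 per arm. With the noncentral t distribution, power is 0.797 at 36 per arm and 0.808 at 37. The stated 37 per arm is reproduced and is not in dispute.

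**2. Precision of the comparison.** Standard error of the difference = 3 × √(2/37) = 0.697 day. The critical t value on 72 degrees of freedom is 1.993, so the smallest observed difference that reaches significance is 1.993 × 0.697 = 1.39 days.

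**3. False-positive rate under a shift, with no true effect.** The test statistic is noncentral t on 72 degrees of freedom with noncentrality *b*/0.697. The rejection rate is P(T > 1.993) + P(T < −1.993).

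| Assumed shift *b* (days) | Noncentrality | Two-sided rejection rate |
|---|---|---|
| 0 | 0 | 5.0% |
| 0.25 | 0.36 | 6.4% |
| 0.5 | 0.72 | 10.9% |
| 1.0 | 1.43 | 29.3% |

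**4. The opposite direction.** If the true benefit is 2 days and the shift runs against treatment, the expected difference is 2 − *b*. Power falls from 80.8% to 69.7% at *b* = 0.25, 56.4% at 0.5 and 29.3% at 1.0.

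**5. What a shift of that size means.** A mean shift of 0.5 day is 0.5 × 37 = 18.5 infant-days of differential dating spread over one arm. A shift of 1.0 day is 37 infant-days, equivalent to every infant in one arm being dated a day later relative to the other arm. The second is a demanding assumption, the first less so.

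These are t-test figures. A rank test also responds to a location shift, but its rates were not computed.

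**The case against.** The strongest reply has five parts.

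- **The definition may exist elsewhere.** The feeding protocol is an attachment that was not supplied. The text says that it outlines signs of intolerance, not that it contains nothing else. A reader might infer that weight gain is defined nowhere. The documents do not support that, and the point is limited to the supplied text. A definition in the attachment would remove the ambiguity, but the absence of any stated masked derivation would remain.
- **The volume threshold is numeric and feeding is standardised.** Both narrow the discretion. They do not remove it, because the weight condition must also be met.
- **No differential is shown.** The weight-gain condition can only delay the date beyond the volume threshold, and bias arises only if that delay differs between arms. Nothing in the documents indicates that it will. This stands: the claim is one of possibility, and the shifts are illustrative.
- **Loss of power from random delay.** A reader might also infer that an undefined criterion adds noise and so lowers power below plan. The documents do not support a figure for this. The SD of 3 days is stated for time to full enteral feeds, the endpoint that includes weight gain, so it plausibly already contains that variation.
- **Full enteral feeds also governs suppository use.** The same term marks when suppositories stop in the treatment arm and when controls may receive them. Redefining it, for example by dropping weight gain, would reach beyond the analysis. This also stands, so the fix is confined to deriving the outcome and leaves the endpoint's composition to the sponsor.

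**Conclusion.** The point holds in this limited form. Followed as written, the supplied text lets a judgement made with knowledge of the arm set the primary outcome date, and it states no safeguard at the point of assessment or abstraction. Whether the route is used, in which direction and by how much cannot be learned from the documents. A reader might infer that the primary comparison will be biased, but the text shows only that it can be.

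On the plan's SD and sample size, an assumed shift of 0.25 day matters little, 0.5 day roughly doubles the type I error, and 1.0 day raises it nearly sixfold (29.3/5 = 5.9). These rates rest on a constant shift, an unchanged SD and the t-test. The sample size of 37 per arm is unaffected. The change should be made because the affected quantity is the primary outcome and the remedy is cheap.

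**What to change.** Before any outcome data are reviewed:

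1. State one operational weight-gain criterion and observation window, chosen by the sponsor. If the attached feeding protocol already has one, cite it.
2. State how the endpoint date is assigned when the two limbs are met on different days.
3. Compute the date for every infant by script from the abstracted volumes and weights, with the arm variable and suppository records withheld.
4. As a sensitivity analysis, report the comparison using the date on which the volume threshold alone was first met.

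This rule is for deriving the outcome only. The suppository instructions in Study Procedures use the same term, so the sponsor must reconcile the two uses. No clinical rule is proposed here.

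**Cost.** Protocol and analysis wording, a short derivation script, and some extra abstraction. Assuming that daily volumes and weights are charted, which the text does not state, 74 infants at about 21 days each gives 74 × 21 = 1,554 infant-days, or about 3,100 values at two per day.

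**Limit.** This removes the unmasked weight-gain call. It does not remove discretion in how unmasked staff advance feeds, which can still affect the day the volume threshold is reached. The report should say so.

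### Randomisation may precede surgery although the arms first differ the day after abdominal closure; drawing the allocation after closure would cheaply avoid exclusions made after randomisation

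*Combined protocol and SAP*

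**What the plan says.** The relevant statements are all in the combined protocol and SAP.

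- **Timing of the draw (Study Procedures).** "Consent and randomization will occur the day of surgery or preceding surgery", and this is done "with the operating surgeon blind to the treatment arm prior to operation". The second phrase makes sense only if an arm may already be assigned when the operation begins.
- **Method (Study Procedures).** After consent, "patients will be randomized (utilizing a block technique) into two groups". No block size is given.
- **First difference between the arms (Study Procedures).** The treatment group receives a suppository "beginning the day after abdominal closure and daily until reaching full enteral feeds". Controls receive none routinely over the same period.
- **Exclusion (Inclusion/Exclusion Criteria).** "Identification of a secondary gastrointestinal abnormality requiring surgical intervention", with no time limit.
- **Target population (Introduction/Background).** Complicated disease means "other concomitant abnormalities of the bowel (termed complicated gastroschisis) that require additional surgical intervention". The trial concerns uncomplicated cases.
- **Rectal bleeding during treatment (Study Procedures).** If it is significant, "suppository administration will be discontinued, and the patient will be removed from the study".
- **Accrual basis (Power Analysis/Recruitment Period).** "The average number of uncomplicated gastroschisis patients admitted to Riley Hospital for Children is approximately 20 per year".

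The plan defines no analysis set.

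**The concern.** The allocation can exist before anyone needs it, and the operation that falls in between can show that the infant does not belong in the trial. The exclusion list points to dropping such an infant. That makes it an exclusion after randomisation, which has to be defended as unrelated to arm and which leaves a gap in a randomisation block. Blinding is stated for the surgeon only, and only up to the start of the operation, so the text does not fully supply that defence. If the infant were kept instead, someone outside the target population would enter the comparison. The documents give no reason for drawing early.

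The lack of an analysis-set rule matters more once treatment has started. Leaving the study for significant rectal bleeding is tied in the text to suppository treatment, so any resulting loss of data would fall mainly on one arm.

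**Working it through.** **1. Order of events.** Study Procedures allows this sequence: consent, draw, operation, abdominal closure, first suppository the next day. The secondary-abnormality exclusion can first be met at the operation, after the draw. Nothing in the plan uses the allocation before the day after closure. Introduction/Background mentions a synthetic graft when primary closure is not feasible, so closure may come later than the first operation and the idle interval may be longer.

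**2. The plan's own figures reproduce.** Inputs from Power Analysis/Recruitment Period: difference 2 days, SD 3 days, two-sided alpha 0.05, power 0.80, 80% enrolment, 85% retention, 20 uncomplicated infants a year, 5.5 years.

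- Two-sample t-test: the required size solves to 36.3 per arm, rounded up to 37. Power at 37 per arm is 0.808.
- Enrolment: 20 × 5.5 × 0.80 = 88, or 44 per arm.
- Completers: 44 × 0.85 = 37.4 per arm, power 0.812.

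**3. Whether the draw timing costs power.** The 88 are counted from uncomplicated infants. An infant found at operation to have complicated disease is not one of them. It adds one draw and one exclusion and leaves the planned completers as they were.

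**4. Size of the problem.** Let k be the number of allocated infants found ineligible at operation. The documents do not give k, so the values below are assumptions. Draws = 88 + k and share excluded = k / (88 + k). Under 1:1 allocation the SD of the between-arm difference in these exclusions is about √k.

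| k (assumed) | Draws | Share excluded | SD of difference |
|---|---|---|---|
| 0 | 88 | 0% | 0 |
| 1 | 89 | 1.1% | 1.0 |
| 3 | 91 | 3.3% | 1.7 |
| 5 | 93 | 5.4% | 2.2 |

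**5. Effect of chance imbalance.** With 74 completers, t-test power is 0.808 at 37 v 37, 0.807 at 36 v 38, 0.806 at 35 v 39 and 0.805 at 34 v 40. Gaps in the blocks do not matter for power at this scale.

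**6. With the draw after closure.** Exclusions found at operation precede randomisation, so their share of the randomised set is 0 for any k. Abnormalities first found after closure are unaffected.

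**The case against.** The strongest reply is that no consequence has been demonstrated. The frequency is unknown, every k above is assumed, and power barely moves. The surgeon is blind beforehand, and an abnormality found at operation predates any study treatment, so excluding on it without knowledge of arm does not bias the comparison. The exclusion list already implies that the infant is dropped. Randomising on the day of surgery also permits a draw after closure. All of this stands, and it limits the point to a cheap improvement.

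A second reply is that a late draw has a risk of its own. Whether an abnormality requires surgery is a judgement, and it would be made after the bowel has been seen but before allocation. If the next assignment in a block could be guessed, enrolment could become selective. This also stands as a small risk. Recording eligibility before the allocation is revealed, concealing the draw and withholding the block size are meant to meet it.

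A third reply is that infants whose abnormality is found after closure remain randomised, so some complicated cases stay in the comparison. That is true, but by then the arm may be known, and keeping them in the assigned arm is safer than excluding them.

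A reader might infer two stronger conclusions that the documents do not support:

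- **That early randomisation leaves the trial underpowered.** This would require taking ineligible infants out of the 44 per arm, but that number is built from uncomplicated infants. Even if they were among the 88, the retention allowance already covers 88 × 0.15 = 13.2 losses.
- **That exclusions at operation bias the comparison.** Blinding before the operation and the absence of any suppository by then make this unlikely.

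**Conclusion.** The point holds as a low-cost design improvement, not as an error in a stated figure. The text permits allocation before surgery, an infant can then become ineligible at operation, and the implied handling is an exclusion after randomisation. Its frequency is not given and may be zero; under assumed counts of 1 to 5 infants it is 1.1% to 5.4% of draws. The risk of bias is small and no loss of the planned 0.80 power is shown. These statements rest on the plan's accrual being counted in uncomplicated infants and on the surgeon in fact being blind until the operation.

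Analysis by assigned arm is worth stating outright, because a departure for bleeding is related to arm in a way that an exclusion at operation is not. The documents do not say that leaving the study removes an infant from the analysis. That is a possible reading, and the plan should rule it out.

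**What to change.** 1. Keep consent before surgery.
2. At abdominal closure, record whether the infant meets the secondary-abnormality exclusion, before any allocation is revealed.
3. Then draw the concealed allocation, before the first scheduled suppository. Do not disclose the block size to clinical staff.
4. State that every infant randomised from then on is analysed in the assigned arm. This includes an infant whose abnormality is found later and one who leaves the study for significant rectal bleeding. Participant Privacy/Data Safety says that all study data come from the medical record, so outcomes can still be collected. Reconcile the Study Procedures wording on leaving the study with this sentence. The clinical stopping rule is not touched.

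**Cost.** Protocol wording, the moment of the draw and one analysis-set sentence. Treatment start, sample size, outcomes and planned tests do not change.

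**Downsides.** The window for the draw is short, between closure and the next day. Some consented infants will not be randomised. Eligibility is judged after the bowel has been seen, hence the concealment and undisclosed block size. A few infants with abnormalities found late stay in the analysis.

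### The plan uses 37 per arm both as the number to enrol, which starts the analysis, and as the number completing out of 44; stopping at 37 enrolled gives power 0.73 to 0.81, so 80% is not assured

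*Combined protocol and SAP*

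**What the plan says.** Two adjacent paragraphs of the Power Analysis/Recruitment Period section give 37 different roles.

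- The power paragraph makes it an enrolment target: "the study will need to enroll thirty-seven (37) in each study arm to detect a difference of two days between groups". It then makes that target the point at which analysis begins: "After reaching this enrollment, that data from each group will be analyzed for normality".
- The recruitment paragraph makes it a number of completers: "Assuming 80% enrollment (i.e. 44 patients enrolled) with an 85% retention rate to completion (i.e. 37 patients completing the study". Neither the 44 nor the 37 is marked as per arm. The same paragraph gives the accrual base, "The average number of uncomplicated gastroschisis patients admitted to Riley Hospital for Children is approximately 20 per year", and the conclusion that "the study period will be approximately 5.5 years".

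Two other places bear on what happens to infants who do not complete. Under Study Procedures, after significant rectal bleeding "suppository administration will be discontinued, and the patient will be removed from the study". Under Participant Privacy/Data Safety, "All data obtained for use in this study will be abstracted from clinical (medical record", so an outcome might still be obtainable for an infant who has left the study. Nothing says how non-completers enter the primary analysis.

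**The concern.** With 85% retention, 37 cannot be both the number enrolled and the number completing. The sentence that treats it as the number enrolled is also the one that ends recruitment and starts the analysis, so the study team would act on that sentence. Read literally, it stops the trial at 74 infants, 14 fewer than the 88 for which the recruitment paragraph appears to provide.

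The power calculation has almost no slack: 37 is the smallest whole number per arm that reaches 80% with a t-test. Any infant without a primary outcome therefore takes the study below its stated power. The missing per-arm label adds a second ambiguity, because on its own the recruitment paragraph could describe a trial of 44 infants in total.

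**Working it through.** **Inputs**, all from the Power Analysis/Recruitment Period section: difference δ = 2 days; SD σ = 3 days (given for the control group, taken as equal in both arms); two-sided α = 0.05; target power 0.80; 20 eligible admissions a year; 80% enrolled; 85% retained; study period 5.5 years.

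**1. Reproduce the 37.** The normal approximation is n = 2[σ(z₀.₉₇₅ + z₀.₈₀)/δ]² = 2[3 × (1.960 + 0.842)/2]² = 35.3, so 36 per arm. The t-test power uses the noncentral t distribution with n₁ + n₂ − 2 degrees of freedom and noncentrality δ / [σ√(1/n₁ + 1/n₂)]. It gives n = 36.3:

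- 36 per arm: power 0.797
- 37 per arm: noncentrality 2/[3√(2/37)] = 2.87, power 0.808

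So 37 per arm is correct as the number **with outcome data**.

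**2. Which enrolment number fits the recruitment paragraph?** Inflating for retention, 37/0.85 = 43.5, which rounds up to 44; conversely 44 × 0.85 = 37.4. Accrual is 20 × 0.80 = 16 a year.

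| Reading | Enrolled in total | Years at 16 a year |
|---|---|---|
| 44 per arm | 88 | 88/16 = 5.5 |
| 37 per arm | 74 | 74/16 = 4.6 |
| 44 in total | 44 | 44/16 = 2.75 |

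Only 44 per arm gives the stated 5.5 years. The recruitment paragraph therefore means 37 completing per arm, and the enrolment sentence and analysis trigger are what disagree with it.

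**3. Power if recruitment stops at 37 enrolled per arm.** At 85% retention, 37 × 0.85 = 31.45 per arm complete, leaving 5.55 per arm who do not. The documents do not say what share of these would still give a primary outcome, so it is varied.

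| Non-completers giving an outcome | Analysed per arm | Power |
|---|---|---|
| None | 31.45 (31 if rounded down) | 0.740 (0.733) |
| Half | 31.45 + 2.775 = 34.2 | 0.776 |
| All | 37 | 0.808 |

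The documents do not give loss by arm either. With 0.15 × 74 ≈ 11 infants lost and no outcome from them, power is 0.740 for a 32 v 31 split, 0.735 for 35 v 28, and 0.727 if all are lost from one arm (37 v 26). If only one arm loses 15% (37 v 31, about 8% overall and so less than the plan assumes), power is 0.770.

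**4. Power if 44 per arm are enrolled.** With 0.15 × 88 ≈ 13 lost and no outcome from them, power is 0.813 for 38 v 37 and 0.801 if all are lost from one arm (44 v 31).

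**The case against.** The strongest reply is that the plan already allows for attrition. The recruitment paragraph raises 37 to 44, and its 5.5 years fits only 88 infants, so the intended trial has its stated power. What remains would be a loosely chosen verb and a missing label. The low power figures also need several things together: stopping at 74, the full 15% loss, no outcome from any non-completer, and either rounding down or a one-sided loss to reach 0.73 rather than 0.74. Stopping at 74 would itself contradict the stated study period. And because data come from the medical record, some or all non-completers may still have a recorded outcome, in which case there is no loss of power.

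Much of this stands. The intended numbers can be recovered, the power loss is conditional, and the top of the range is no loss at all. But recovering the intention takes a back-calculation from the study period, while the explicit instruction on when to stop and analyse says something else. No sentence says which number governs. The reply limits the weight of the point; it does not remove the contradiction.

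**Conclusion.** The concern holds, as an internal inconsistency and not as a miscalculation. The two paragraphs give different enrolment numbers, 37 and 44 per arm, and the one tied to the analysis trigger is the one that does not fit the plan's own retention and study period.

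Followed literally, it gives power between 0.73 and 0.81 instead of an assured 0.80, a shortfall of at most about 0.07 below target. The low end assumes that the plan's 85% retention applies to the 74 enrolled and that non-completers contribute no primary outcome; the high end assumes that all of them contribute. Enrolling 88 keeps power at 0.80 or above at 85% retention, even if every loss falls in one arm.

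These figures are for the t-test with SD 3 in both arms. If the Wilcoxon fallback were used on near-normal data (taking its asymptotic relative efficiency as 3/π), power would be slightly lower: about 0.79 with 37 analysed per arm and about 0.71 with 31. That does not alter the conclusion. The point should be fixed before anyone relies on the trigger to close recruitment.

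**What to change.** In the Power Analysis/Recruitment Period section:

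- State that 37 infants per arm (74 in total) with the primary outcome are required and that, allowing for 85% retention, 44 per arm (88 in total) will be enrolled, taking about 5.5 years at 16 a year.
- Tie the analysis to the point at which 44 infants per arm (88 in total) have been enrolled and followed for the primary outcome, instead of to enrolment of 37 per arm.
- Mark the 44 and the 37 in the recruitment paragraph as per arm.

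A fixed 44 per arm yields 37 outcomes only if at least 37/44 = 84% provide one, so the plan should also say whether infants who leave the study still contribute a primary outcome from the medical record.

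If 37 enrolled per arm is really intended, restate the period as about 4.6 years, and give the power for a named assumption about non-completers: about 0.73 to 0.74 if none contribute, 0.78 if half do, 0.81 if all do.

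The cost is wording only. The stated 5.5 years already covers 88 infants, so no recruitment is added to it.

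### Allocation is blocked over about 5.5 years but both primary tests ignore enrolment time; a steady drift would make them conservative, and one prespecified date term would recover the lost power

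*Combined protocol and SAP*

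**What the plan says.** Under Study Procedures, the combined protocol and SAP states that "patients will be randomized (utilizing a block technique) into two groups: the treatment group and the control group". It gives neither block size nor stratification factors. The same section introduces common care for all participants: "A newly developed study-specific standardized feeding protocol that has been adopted by all pediatric general surgeons". Part of nutritional care is left open: "Weaning of TPN during advancement of enteral feeds will be based upon attending preference".

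Under Power Analysis/Recruitment Period, the number of eligible infants "admitted to Riley Hospital for Children is approximately 20 per year", and "the study period will be approximately 5.5 years". The sample size is 37 per arm for a 2-day difference, with SD 3 days, power 0.8 and two-sided alpha 0.05. For the analysis, "student's t-tests will be performed to determine significance for the primary outcome variables", with a Wilcoxon rank-sum test if normality fails. No block term, enrolment date or other covariate appears anywhere in the text.

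**The concern.** Blocked allocation balances the arms over calendar time. A gradual change in time to full feeds then adds almost nothing to the true sampling variance of the arm difference, because both arms carry it equally. A two-sample t-test or rank-sum test treats the arms as simple independent samples and counts the change as noise. Its standard error is then larger than the real one, the interval is too wide, and the rejection rate under the null falls below 5%.

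A drift is plausible here: accrual is long, there is one hospital, the feeding protocol is new at the start, and some care is not standardised. At stake is precision that the blocked design has already provided. The trial has little to spare, with calculated power of 0.808 against a target of 0.80.

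**Working it through.** **1. The plan's own figure.** Inputs from Power Analysis/Recruitment Period: difference 2 days, SD 3 days, two-sided alpha 0.05, power 0.80.
- Normal approximation: n = 2 × 3² × (1.960 + 0.842)² / 2² ≈ 35.3, so 36 per arm.
- Noncentral t: 36.3, so 37 per arm, with power 0.808. The stated 37 is reproduced.
- Accrual: 37 / 0.85 = 43.5, so 44 per arm, and 2 × 44 = 88 = 20 × 0.8 × 5.5. The phrase "Assuming 80% enrollment (i.e. 44 patients enrolled" is therefore read as per arm.

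**2. Approximate effect of a linear drift.** Let the mean change by D days, evenly over accrual. D is an assumption, taken over 0 to 6 days. The variance of the trend across infants is D²/12. If 3 days is the SD among infants enrolled at the same time, the unadjusted standard error exceeds the true one by the factor √(1 + D²/(12 × 9)):
- D = 2: √1.037 = 1.018
- D = 4: √1.148 = 1.072
- D = 6: √1.333 = 1.155

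At 37 per arm the true standard error is 3 × √(2/37) = 0.697, so a 2-day effect is 2.87 standard errors. Power is approximately Φ(2.87 − 1.99 × factor), which gives 0.809, 0.799, 0.768 and 0.714 for D = 0, 2, 4 and 6. With adjustment for date it stays at 0.809.

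**3. Simulation, SD 3 excluding the trend.** 10,000 trials per scenario, 76 infants (74 is not a multiple of 4), permuted blocks of 4 (assumed). Adjusted means a linear model with arm and enrolment time. Monte Carlo standard error is about √(0.05 × 0.95/10,000) = 0.002 for type I error and √(0.8 × 0.2/10,000) = 0.004 for power.

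| D (days) | t-test SE / true SD | Type I: t | Type I: Wilcoxon | Type I: adjusted | Power: t | Power: Wilcoxon | Power: adjusted |
|---|---|---|---|---|---|---|---|
| 0 | 0.685 / 0.681 | 0.048 | 0.047 | 0.048 | 0.821 | 0.800 | 0.821 |
| 2 | 0.699 / 0.684 | 0.044 | 0.043 | 0.049 | 0.809 | 0.788 | 0.818 |
| 4 | 0.739 / 0.692 | 0.033 | 0.033 | 0.047 | 0.774 | 0.751 | 0.816 |
| 6 | 0.798 / 0.685 | 0.022 | 0.022 | 0.046 | 0.717 | 0.685 | 0.811 |

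For the t-test, the power lost is about 1, 4 and 9 points.

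**4. Simulation, SD 3 including the trend.** Power, t-test against adjusted: 0.816 and 0.816 (D = 0), 0.820 and 0.831 (D = 2), 0.837 and 0.879 (D = 4), 0.871 and 0.947 (D = 6). Type I error of the t-test at D = 2, 4 and 6 is 0.043, 0.035 and 0.016. The loss is about 1, 4 and 8 points, but unadjusted power never falls below 0.80.

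**5. Sensitivity at D = 4, SD excluding the trend.** Power, t-test against adjusted: blocks of 2, 0.775 and 0.822; blocks of 8 (72 infants), 0.752 and 0.797; random loss from 88 to 74 infants, 0.755 and 0.801. The gap does not depend on the unstated block size.

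**6. Another shape of trend.** If a 4-day fall is complete within the first 15% of enrolment, a linear date term gains under 1 point: 0.828 and 0.836 (SD including the trend), 0.790 and 0.798 (SD excluding it).

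**7. Alternative adjustments.**
- A van Elteren test with yearly strata loses power against plain Wilcoxon when there is no trend: 0.765 against 0.795 in one set of runs, 0.767 against 0.807 in another that allowed for losses. It still loses at 2 days (0.786 against 0.801; 0.762 against 0.779) and gains only from about 4 days (0.831 against 0.817; 0.822 against 0.802).
- Fixed block effects, once losses break up the blocks, give 0.777 with no trend (t-test 0.804) and 0.773 at D = 4 (single date term 0.801).

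**The case against.** The strongest reply is that nothing here is wrong. An unadjusted test after blocked randomisation is common and valid, the estimate is unbiased, and any departure from 5% is towards caution. A reader might infer that the plan's alpha and power are misstated, or that false positives become more likely. The documents support neither: 37 per arm is correct for the stated inputs, and the type I error under drift lies below nominal.

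A reader might also infer that any time trend wastes meaningful power, or that the new feeding protocol shows that a trend exists. Neither follows. The documents give no trend at all. The feeding protocol is standardised, adopted by all the surgeons and applied to every participant, so it is also a measure to hold care constant. Being new suggests at most a learning period, and a short one leaves a linear date term with almost nothing to recover. The drifts at which the loss is material are at least twice the 2-day effect that the trial is designed to detect.

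These points stand, and they limit the finding to an efficiency gain that depends on a sustained drift. They do not remove the case for a date term that shows no power cost when the drift is absent.

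**Conclusion.** The point holds as an optional improvement. If time to full feeds drifts linearly over accrual, the planned tests are conservative: type I error is about 0.044, 0.033 and 0.02 for drifts of 2, 4 and 6 days, and the t-test loses about 1, 4 and 8 to 9 points of power against a date-adjusted model. At 2 days or less, or with a short early learning curve, the loss is negligible.

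Whether the t-test misses its target depends on what the SD of 3 days describes, which the documents do not say. If it includes the trend, power stays at or above 0.80 and the loss is only relative. If it excludes the trend, power is about 0.77 at 4 days and 0.72 at 6 days. The figures rest on assumed linear drifts, normal outcomes and assumed block sizes.

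**What to change.** **Normal branch.** Replace the t-test with the arm difference, its confidence interval and p-value from a linear model containing arm and date of enrolment as a single linear term. The cost is one sentence in the analysis paragraph and one degree of freedom; without drift there is no visible loss of power (0.821 in both analyses). Enrolment date is known for every infant.

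**Non-normal branch.** Keep the Wilcoxon test, or name a rank-based analysis of covariance with the same enrolment-date term; the latter was not simulated here. Do not use a van Elteren test with yearly strata, which costs about 3 to 4 points of power when there is no trend. Fixed block effects are also not advised, since they lose power once infants drop out.

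**Timing.** State the choice before outcomes are seen by arm. If they have already been seen, keep the planned test as primary and report the date-adjusted model as a sensitivity analysis. The sample size needs no change.
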